and ≥ 0.80 large).⁹⁹ Per stakeholder request, we will conduct post-hoc mixed-effects regression to calculate the percentage of participants who increased their Behavior Change score, Action scores, or both Behavior Change and Action scores from baseline (i.e., estimated slope > 0) by study arm; p-values adjusted to a significance of 0.017.

1678

1679 For moderator analysis, we will test for interactions by adding interaction terms to the group by 1680 time variable for health literacy (limited versus adequate) controlling for prior ACP 1681 documentation and clustering effects by clinician. All other interaction terms are adjusted for 1682 health literacy (randomization blocking variable) prior ACP documentation and clustering effects 1683 by clinician. Additional interaction terms to be added to the group by time variable include 1684 language (i.e., English versus Spanish), control preferences for decision making (i.e., makes 1685 own decisions versus doctor makes decisions), age (i.e., < 65 years versus \geq 65 years of age), 1686 sex/gender (i.e., self-reported man versus woman), race/ethnicity (i.e., white versus non-white), 1687 health status (i.e., good-to-excellent versus fair-to-poor), presence of a potential surrogate (i.e., 1688 yes versus no), internet access at home (i.e., yes versus no), and, for Spanish-speakers, 1689 patient-clinician language (concordance vs. discordance). A p-value for interaction <0.05 is 1690 considered significant. 1691

Missing data for the primary outcome will be assessed. If there is 10% or more of missing data, we will use a mean imputation approach. All available data will be included in mixed-effects models. We will assess whether any research staff member became unblinded during follow-up assessment and conduct sensitivity analysis as needed.

1696

1697 SAMPLE SIZE AND POWER CALCULATIONS

1698 We will measure a full range of ACP behaviors including discussions. However, written advance 1699 directive completion of legal forms is a primary outcome and is the most well-studied.¹⁰⁰ Power

1700 from longitudinal analyses with repeated measures will be stronger, but to be conservative, we consider power for a single post-intervention time point (e.g., 15 months). A recent meta-1701 1702 analysis of written advance directive documentation studies demonstrated a pooled effect size of 0.50 (95% CI; 0.17 -0.83),¹⁰⁰ as did an RCT of an ACP workbook that included both behavior 1703 change constructs and a social work visit,¹⁰¹ and our prior RCT of an easy-to-read AD at ZSFG 1704 which showed an increased AD completion rate from 7% to 15%.⁸ Because both the 1705 1706 intervention and control arm will receive the easy-to-read advance directive, we assume that 1707 both arms will have an advance directive completion rate of $\leq 15\%$. Based on prior studies, we 1708 assume PREPARE will result in additional benefit of advance directive completion with a 1709 minimum effect size of 0.5 (two-fold increase) above 15%. A sample of 350, (175 per arm), will 1710 afford us 92% power (2-tailed alpha of 0.05) to detect a difference of advance directive 1711 completion rates of 15% in controls vs. 30% in the PREPARE arm and 80% power to detect a difference of 15% vs. 27%. Power is also expected to be strong for the ACP behavioral change 1712 scale outcomes (preliminary data demonstrated a pre-to-post improvement of 0.5 SD).²⁷ With a 1713 1714 conservative assumption that controls will improve by 0.1 to 0.2 SD, we will have 85% to 98% 1715 power, respectively, to conclude that the improvement is better in the PREPARE arm. We 1716 expect a 15% drop out rate at 12 months based on our prior randomized, controlled trial at ZSFG,⁸ and will therefore attempt to recruit 402 patients, or 201 in each arm for each language 1717 1718 (English and Spanish) for a total recruitment of 804 patients.

1719

Our sample size will also allow adequate power to detect clinically important interactions based on potential moderators (literacy, control preferences, language concordance) for our outcomes. In a prior trial of an easy-to-read advance directive in the same patient population with only 200 patients, we found significant interactions for literacy.⁸ Thus, if we consider the power scenario of the control group ACP documentation rate of 15% and the PREPARE group of 28%, and suppose the control group rate is the same (15%) for both levels of the moderating factor, then

1726 for a moderating factor split of 1:1, we would have 80% power to detect an interaction. If the 1727 PREPARE arm ACP documentation rate is 18% for one level of the factor and 40% for the 1728 other, this corresponds to a relative rate of ACP documentation of 2.2 times as high for one 1729 level of the factor compared to the other. A 2:1 split of the moderating factor still allows 1730 detection of a 2.4-fold increase in the relative rate of documentation. Power to detect 1731 interactions will likely be stronger for continuous outcomes (e.g. engagement/behavioral scales). 1732

ETHICS AND ADVISORY COMMITTEES 1733

1734 This study is approved by the University of California, San Francisco (UCSF) (IRB reference 1735 #13-10847). This study is guided by a Patient-Clinical Stakeholder Advisory Board that is 1736 comprised of patients and patient advocates (including native Spanish-speakers), surrogates, 1737 and ZSFG/SFHN primary care clinic staff and medical directors. It is also guided by a DSMB 1738 consisting of 4 experts in randomized trials, human subjects research and consent, vulnerable 1739 populations, palliative care, advance care planning, and biostatistics. Both advisory groups 1740 reviewed and approved all study protocols and related materials. In addition, we continue to 1741 meet with both groups every 4-6 months to review the progress of the trial, make suggestions 1742 for recruitment, review any potentially adverse events, and ensure that we are following our 1743 study protocols in a way that protects vulnerable patient populations.

1744

1745 **HUMAN SUBJECTS PROTECTIONS**

1746 Protection of the rights and welfare of participants:

1747 All study staff are required to take annual training regarding the rights and protections of 1748 research participants. Additionally, weekly study team meetings will ensure that all study staff 1749 are following the research protocol and that all study participants are consented according to 1750 our study protocol.

1752 Furthermore, our consent process ensures that study participants have a clear understanding of 1753 the study and understand that they can choose to not participate in the study at any point in 1754 time, and that the care they receive will not be affected by declining to participate in our study. 1755 Our consent process involves using a consent form written below a 6th-grade reading level, 1756 reading the form to potential subjects verbatim, allowing time for questions and discussion, and 1757 then assessing comprehension using teach-to-goal. If guestions are not answered correctly, 1758 repeated education and reassessment of comprehension are continued until complete 1759 comprehension is achieved. If subjects take more than three passes through the 1760 comprehension assessment, formal assessment for cognitive impairment will be completed. If 1761 patients are found to be cognitively impaired, they are excluded from the study. If they are not 1762 cognitively impaired, we will re-do teach back once more, after which the participant will be 1763 deemed ineligible for the study if they are unable to demonstrate comprehension of the study. 1764

Additionally, we include UCSF Clinical Research Office contact information on all consent forms
as required for all non-biomedical studies.

1767

1768 **Steps taken to minimize risks to subjects:**

We have developed a modified research consent process that has been shown to be successful in vulnerable patient populations as described above.²⁹ All study fliers, consent forms, and questionnaires are read to the subjects in their entirety by native English- and Spanish-speaking research staff. Participants are reminded that they can opt out of the study at any time. All study materials are in an easy-to-read (5th grade reading level, large 14-point font) format. The consent materials and the study interviews are conducted in the language the participant is most comfortable speaking (English or Spanish).

1776

1777 This study will employ research assistants who are fluent in English or Spanish. Only fluent 1778 research assistants will be in contact and will communicate with Spanish-speaking participants. 1779 We will also ensure that all study materials are accurately translated into Spanish by having 1780 them initially translated from English to Spanish by native Spanish- speakers. We will then have 1781 them back translated into English to ensure accuracy. Finally, we will have the final translated 1782 documents reviewed for accuracy by third party native Spanish- speakers. To help participants 1783 follow along during the interview, they may review a large font Participant Version of the survey 1784 at baseline and all follow-ups that can be reviewed while the research assistant is asking 1785 research questions verbatim. We use 14-point font and color-coded, standardized, large font 1786 response options to help with understanding. 1787 1788 Data security: 1789 - Data are stored securely in the encrypted, secure UCSF MyResearch environment 1790 - Data are coded; data key is kept separately and securely 1791 - Data are kept in a locked file cabinet 1792 - Data are kept in a locked office or suite 1793 - Electronic data are protected with a password 1794 - Data are stored on a secure network 1795 - Data are collected/stored using REDCap or REDCap Survey 1796 1797 Measures to ensure confidentiality and protect identifiers from improper disclosure 1798 Risks to subjects are minimal and may include loss of confidentiality and psychological 1799 discomfort about discussing end-of-life issues. Subjects are assured that their answers to study 1800 questions will not be directly linked to their names. Instead, any identifying information is coded 1801 and separated from the data. The identifying information will only be known to the primary 1802 investigators but will not be used in data analysis. In addition, signed consent forms are kept in

1803 locked file cabinets and kept separate from the data collection instruments. Study subjects are 1804 also reminded that the information obtained will not be shared with their providers except in non-1805 identifying aggregate form at the end of the study. We also make clear that the responses to the 1806 PREPARE guide are only for research purposes and will not be shared with their clinicians or 1807 put in their medical record.

1808

We will store all study materials in locked offices and locked storage cabinets. We will utilize
UCSF MyResearch and REDCap to enter and maintain data in a secure environment. In order
to be more environmentally-conscious, we will attempt to use the LiveCapture function of
RedCap and thus reduce the use of paper resources. We will retain the use of paper surveys in
case the RedCap system is down. These paper files are stored in secure, locked research
offices in secure, locked file cabinets.

1815

1816 As some of the questions concerning end-of-life may cause psychological discomfort for some 1817 study subjects, subjects are reminded at the beginning of the interview of their right to refuse to 1818 answer any and all questions and their right to terminate the interview at any time. We will also 1819 reassure subjects that if they choose not to be in the study or choose to terminate the interview, 1820 it will not change the medical care that they normally receive from their clinic or their clinician. In 1821 addition, we will reiterate that the information shared within the research interview will not be 1822 shared with their clinicians or used in medical care. However, subjects can take home a copy of 1823 the PREPARE guide with them and bring it back to their clinicians if they wish. Subjects are 1824 given the name and number of the primary investigator and may call if they have questions or 1825 are concerned about their participation in the study.

1826

1827 **Required reportable information:**

1828 As these interviews may be completed in people's home and, in the interviews, we are asking patients to describe their experiences and opinions, it is possible that reportable events such as 1829 1830 elder abuse, suicidal or homicidal ideation may be detected. If they are detected, they will be 1831 handled according to the American Psychological Association code of ethics. If elder abuse is 1832 suspected, the participant will be encouraged to take steps to ensure their safety. They will be 1833 offered contact information for local supportive services and informed that the concerns will be 1834 discussed with the elder abuse hotline for assistance. When there are concerns about self-harm 1835 or harm to others, severity of harm will be assessed. Participants will be offered local support 1836 services and officials will be notified as necessary.

1837

1838 Patient Depression/Anxiety Protocols

With input from the Patient-Clinician Stakeholder Advisory Board, and to err on the side of caution, we created a flow diagram with detailed instructions, including study scripts and contact names and telephone numbers for research staff to use in the event scored in the moderately severe depression or anxiety range on the PHQ-8 and GAD-7 or a participant expressed suicide ideation.

1844

1845 DATA SAFETY MONITORITY PLAN

1846 Monitoring will focus on recruitment, baseline comparability of treatment groups, protocol 1847 adherence, completeness of data, accrual of primary endpoint data, safety, and follow-up rates. 1848 This monitoring will provide the basis for monthly review by the study investigators, review by 1849 the ZSFG Patient-Clinician Advisory Committee, and Data Safety and Monitoring Board 1850 (DSMB), and yearly reporting to our IRBs. We will implement methods of verifying entered data 1851 and of quality control. All study materials data are kept on secure, password-protected, 1852 encrypted servers. All consent materials and any identifying information are kept in locked 1853 cabinets within locked offices, on password-protected, encrypted servers, on card-key protected

1854 research floors. [name], will be directly responsible for identifying and immediately reporting 1855 all adverse events to the IRBs Privacy Officers, and funding agency as appropriate. The ZSFG 1856 Patient-Clinician Advisory Committee will ensure participant safety in the clinic and will meet up 1857 to 4 times per year. The formal DSMB includes 4 experts in randomized trials, human subjects research and consent, vulnerable populations, palliative care, advance care planning, and 1858 1859 biostatistics. The DSMB will review and approve the research protocol and plans for data and 1860 safety monitoring; and assess data quality; participant recruitment, accrual and retention; 1861 baseline comparability of treatment groups, accrual of primary endpoints; and participant safety 1862 (e.g., adverse events, protocol violations). They will also develop stopping rules for the trial. The 1863 DSMB will meet up to 4 times per year.

1864

1865 CHARTER OF DATA SAFETY MONITORING BOARD

1866 The Data and Safety Monitoring Board (DSMB) will act in an advisory capacity to the National 1867 Institute of Aging (NIA) Director to monitor participant safety, data quality and evaluate the 1868 progress of the study. [name], University of California, San Francisco is conducting the 1869 "Improving Advance Care Planning by Preparing Diverse Seniors for Decision Making" study 1870 under a R01 funded by the National Institute of Aging. The DSMB for this study includes 2 outside clinicians with expertise in RCTs and an outside biostatistician. The NIA program officer 1871 1872 is also included. The DSMB will review and approve the research protocol and plans for data 1873 and safety monitoring; and assess data quality; participant recruitment, accrual and retention; 1874 baseline comparability of treatment groups, accrual of primary endpoints; and participant safety 1875 (e.g., adverse events, protocol violations). They will also develop stopping rules for the trial. The 1876 DSMB will meet 2 and up to 4 times per year.

1877

1878 **DSMB Responsibilities**

1879 The DSMB responsibilities are to:

review the research protocol, informed consent documents and plans for data safety and
 monitoring;

- advise the NIA on the readiness of the study staff to initiate recruitment;
- evaluate the progress of the trial, including periodic assessments of data quality and
- 1884 timeliness, recruitment, accrual and retention, participant risk versus benefit, performance of
- 1885 the trial sites, and other factors that can affect study outcome;
- consider factors external to the study when relevant information becomes available, such as
 scientific or therapeutic developments that may have an impact on the safety of the
- 1888 participants or the ethics of the trial;
- review study performance, make recommendations and assist in the resolution of problems
 reported by the Principal Investigator;
- protect the safety of the study participants;
- report to NIA on the safety and progress of the trial;
- make recommendations to the NIA and the Principal Investigator concerning continuation,
- termination or other modifications of the trial based on the observed beneficial or adverse
- 1895 effects of the treatment under study;
- if appropriate, review interim analyses in accordance with stopping rules, which are clearly
- defined in advance of data analysis and have the approval of the DSMB;

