require staff to use approved study scripts when speaking to patients. These study scripts and all study materials used for recruitment are vetted, updated and approved by both our patient advisory and clinical advisory boards. All materials and study scripts are written at a 5th grade reading level and are provided to patients in their preferred language (i.e., English or Spanish).

1334 CONSENT PROCEDURES

We use a modified consent process that several co-authors designed for vulnerable populations.^{28,29} Consent forms written at the 5th grade reading level are provided and read to participants in English or Spanish. This review is then followed by standardized "teach-to-goal" questions to ensure understanding. If potential participants cannot correctly complete the teachback process after 3 attempts, the patient is deemed ineligible.

1340

1341 The consent form is approved by the UCSF and ZSFG Institutional Review Boards, the 1342 patient/clinical advisory board, and the Data and Safety Monitoring Board (DSMB). The consent 1343 form states the following for the purpose of the study: "Why is this study being done? 1344 Sometimes patients and their families have to make hard medical decisions. We want to design 1345 and test an easy-to-understand handout to help. This handout will help people think about their 1346 values, or what is most important to them in their life. It will also help prepare patients to make 1347 medical decisions." We use the word "handout" because, in pilot testing, both groups are given 1348 handout materials and written advance directives. For randomization we explain, "We will ask 1349 you to look over a handout and answer some questions about your experience with making 1350 medical decisions. There will be two groups that will be given different handouts. You will have a 1351 50/50 chance of being in either group."

1352

1353 Due to exclusions based on several missed baseline appointments and for staff safety and the 1354 need to exclude or withdraw participants who were intoxicated, psychotic, or threatening, the

1355 consent also explains, "We also may ask you to stop taking part in this study if we feel it is in

1356 your best interest or if you do not follow the study rules."

1357

1358 It was determined with our Patient-Clinician Advisory Board that clinicians of patients should be

- 1359 contacted in the event that the patient reports severe depression or anxiety. Our DSMB agreed

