1434 A statistician not involved in recruitment or data collection uses a computer-based random number generator to create a randomization scheme using block randomization by health 1435 1436 literacy (adequate health literacy versus limited health literacy, as determined by a validated 1437 guestion concerning confidence with medical forms).⁷¹ Random block sizes of 4, 6, and 8 are used to ensure an equal number of patients with limited health literacy in each group. 1438 1439 Randomization information is associated with a unique patient identification number and is kept 1440 separate from other patient data. Due to the need to secure interview rooms for the duration of 1441 the baseline questionnaire and intervention (i.e., approximately 2 hours for the AD-only arm and 1442 3 hours for the PREPARE arm), randomization occurred prior to scheduling a baseline 1443 interview. 1444 1445 1446 BLINDING 1447 Clinicians are blinded to patient group assignment. Although we obtain clinicians' permission to 1448 recruit their patients, the interventions are not described, and no clinician education is provided. 1449 Participants could not be blinded to the intervention; however, they are told during consent there 1450 is a "50/50 chance" of getting one of two different ACP guides, and the non-assigned 1451 intervention is not described. Because each group obtains ACP materials, such as the easy-to-1452 read advance directive, blinding is enhanced. The research assistant who administers the 1453 intervention cannot be blinded to the study arm, but all follow-up outcome assessments are 1454 conducted by different and blinded staff. At the start of all follow-up interviews, participants are 1455 reminded not to discuss the study materials they reviewed with assistants recording if they 1456 became unblinded. If unblinding occurs, a different blinded assistant conducts all subsequent

interviews.

1458

1459 INTERVENTION FIDELITY

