1649 Our primary analyses will compare change in ACP documentation between study arms from 1650 baseline to 15 months. Secondary outcomes will include ACP Engagement with respect to 5 1651 ACP Actions (yes/no and a 0-25-point scale) and behavior change scores (average 5-point 1652 Likert scores) from baseline to 1 week, and 3, 6, and 12 months. Variables will be assessed for distributional and outlier values using standard summary statistics. Baseline comparability will 1653 1654 be assessed between groups using unpaired t-tests, Chi-square tests or Fisher's exact tests. 1655 Using t-tests or Chi-squared tests, we will also compare patient's age and self-reported gender 1656 between those who refused versus those who enrolled and differences between arms of those 1657 who withdrew versus those who did not. We will use intention-to-treat analysis using SAS 1658 version 9.4 (SAS Institute Inc.) and STATA 15.0 (College Station, TX). All p-values will be 2-1659 tailed and set at .05 for the primary outcome and Bonferroni adjusted for secondary patient-1660 reported outcomes. In addition, because of differences in ACP engagement among English and Spanish speakers,⁸ and based on preferences of our stakeholders and granting agencies, we 1661 1662 decided, a priori, to analyze our results overall and stratified by English and Spanish language. 1663 To compare outcomes between the two arms longitudinally, we will use mixed effects linear, 1664 Poisson, or negative binomial regression for continuous measures and mixed effects logistic regression for dichotomous measures. The mixed effects models will include fixed effects for the 1665 1666 primary modeling terms of time (baseline and 15 months for ACP documentation and baseline 1667 and 1 week, 3 months, 6 months, and 12 months for ACP Engagement with time modeled using 1668 dummy variables to allow for non-linearity); arm (AD-only versus PREPARE); an interaction 1669 term of study arm and time; and a random effect for subjects. We will adjust for the randomization blocking factors limited vs. adequate literacy,⁹⁸ and any predictor variables that 1670 1671 differ between arms. All models also will also be adjusted for baseline ACP documentation and will include random physician intercepts to account for nesting of patients within physicians. We 1672 1673 will use standardized, clinically meaningful effect sizes (i.e., 0.20-0.49 small, 0.50-0.79 medium,

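### Language is not a prespecified adjuster in the pooled models or the race/ethnicity moderator model, so a race/ethnicity interaction can partly reflect language; the remedy is free and the gain modest

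*Combined protocol and SAP*

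**What the plan says.** All references are to the final protocol.

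- **Randomization Procedures.** A statistician uses a computer-based random "number generator to create a randomization scheme using block randomization by health" literacy. Blocks of 4, 6 and 8 are "used to ensure an equal number of patients with limited health literacy in each group". Language is not named as a stratum. Allocation is 1:1; Consent Procedures tells patients of a "50/50 chance of being in either group".
- **Sample Size and Power Calculations.** The calculation starts "A sample of 350, (175 per arm), will" and leads to a recruitment target of 402, "or 201 in each arm for each language", 804 in all.
- **Statistical Analysis Plan, main models.** Results are to be given overall and separately for English and Spanish speakers, partly "because of differences in ACP engagement among English and Spanish speakers". The mixed models contain arm, time and arm-by-time, with adjustment for literacy, baseline ACP documentation and whichever predictors turn out to differ between arms, plus random intercepts for subject and physician. Language is not named as a covariate.
- **Statistical Analysis Plan, moderators.** Language (English or Spanish) is listed as one of the terms to be interacted with group by time. So is "race/ethnicity (i.e., white versus non-white"). Every moderator model other than the literacy one is adjusted for "health literacy (randomization blocking variable) prior ACP documentation and clustering effects" by clinician. Language is not among these adjusters.
- **Research Aims and Study Hypotheses.** Race/ethnicity is one of the moderators named in Aim 2.

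**The concern.** Language determines which of the two cohorts a patient belongs to, and the SAP itself cites a difference in engagement between the languages. It is an eligibility item, so it is known for everyone before randomisation. Yet whether it enters the pooled models depends on what the baseline comparison happens to show, so the covariate set of the primary model is not fixed in advance.

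The larger issue is the race/ethnicity moderator. Half the planned sample is Spanish-speaking. If the racial mix differs between the languages and PREPARE works better in one language than in the other, a model with arm-by-race but no arm-by-language credits part of the language difference to race. The trial could then report, under a stated aim, a race/ethnicity interaction that is partly a language interaction.

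**Working it through.** **1. The plan's own figures.** With 175 per arm and two-sided alpha 0.05, the normal approximation with pooled variance gives 92.3% power for 15% vs 30% and 79.0% for 15% vs 27%. The plan states 92% and 80%, so these agree. The target also follows: 350 × 1.15 = 402.5, hence 402 per language and 201 per arm.

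**2. Imbalance by language with literacy-only blocking.** With 804 patients, 402 in each language and 402 in each arm, the number from one language in one arm is approximately hypergeometric:

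SD = √(804 × 0.5⁴) = 7.09; 201 ± 1.96 × 7.09 gives about 187 to 215.

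A simulation with permuted blocks of 4, 6 and 8 (3,000 runs per setting) agrees. Languages enrolled together, and the limited-literacy shares were assumed at 30%/50%, 40%/40% and 20%/60% (English/Spanish).

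| Scheme | SD | 95% range | Exactly 201 |
|---|---|---|---|
| Literacy only | 6.4-7.1 | 187-215 (189-213 for 20%/60%) | about 6-7% |
| Literacy × language | 0.8 | 200-202 | 52% |
| Literacy only, one language enrolled after the other | 0.8 | 200-203 | 50% |

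**3. Cost in power within a language**, after 15% loss (201 × 0.85 = 170.85 per arm):

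| Split | 15% vs 30% | 15% vs 27% |
|---|---|---|
| 201:201 | 91.7% | 78.0% |
| 215:187 (either direction) | 91.5-91.6% | 77.5-78.0% |

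The loss at the edge of the 95% range is under about 0.5 point.

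**4. Shift in the pooled comparison.** For a crude comparison at one time point, shift = gap × (215 − 187)/402 = gap × 0.0697. The documents give no documentation rate by language. For an assumed gap of 5, 10 or 15 points the shift is 0.35, 0.70 or 1.04 points, against planned differences of 12 to 15 points. The planned model estimates arm-by-time, which largely absorbs a language difference that is constant over time. Only a different *change* over time by language would move the estimate.

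**5. Mixing of race/ethnicity with language.** Let q_E and q_S be the non-white shares of English and Spanish speakers, with equal cohorts. The Spanish-speaking share is

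- among non-white patients: s_NW = q_S / (q_S + q_E);
- among white patients: s_W = (1 − q_S) / [(1 − q_S) + (1 − q_E)].

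The sample-size section's moderator scenario has PREPARE rates of 18% and 40% with 15% in controls, that is, effects of 3 and 25 points. Suppose these are the English and Spanish effects and race has no effect of its own. The apparent non-white minus white difference in effect is then (25 − 3) × (s_NW − s_W) points:

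| q_E | q_S = 50% | q_S = 70% | q_S = 90% | q_S = 100% |
|---|---|---|---|---|
| 50% | 0.0 | +4.6 | +10.5 | +14.7 |
| 60% | −2.2 | +2.4 | +8.8 | +13.8 |
| 70% | −4.6 | 0.0 | +6.9 | +12.9 |

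For example, with q_E = 50% and q_S = 90%: s_NW = 0.9/1.4 = 0.643, s_W = 0.1/0.6 = 0.167, and 22 × 0.476 = 10.5. If the larger effect were in English speakers, the signs would reverse. All values of q_E and q_S are assumptions.

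**The case against.** A reader might infer that the moderator analysis ignores language. It does not: language has its own interaction with group by time, patient-clinician language concordance is a further moderator for Spanish speakers, and language-stratified results are planned. For the same reason it would be too strong to say that race/ethnicity cannot be separated from language. What remains is narrower: a separate language interaction does not adjust the race/ethnicity one. The stratification sentence could be read as covering the moderator models too, but the SAP does not say so.

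A reader might also infer that the plan guarantees 201 per arm in each language and fails to secure it. The text only says the team will attempt to recruit that number. Imbalance also depends on enrolment order and list structure, neither of which is stated. It cannot bias the language-stratified comparisons.

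Other points stand in part:

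- The rule on predictors that differ between arms is a route by which language could enter the pooled models. It is data-driven, so it does not amount to prespecification.
- The difference that the SAP cites concerns engagement, which is the secondary survey outcome, whereas the primary outcome is chart documentation. That language predicts documentation is plausible but not shown.
- An interaction that is not adjusted for language is a legitimate description of whether efficacy varies by race/ethnicity, which is what Aim 2 asks. This is a reason to report the adjusted model beside the planned one, not in its place.
- The mixing needs both an arm-by-language interaction and a different racial mix by language, and the documents establish neither.

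**Conclusion.** The point holds in limited form. Language is neither a randomisation stratum nor a prespecified covariate in the pooled models, and the race/ethnicity moderator model does not adjust for it.

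The consequence that matters is for interpreting the race/ethnicity moderator. Under the 18%/40% scenario, with 50-70% of English speakers and 90-100% of Spanish speakers non-white, about 7 to 15 points of the 22-point language contrast would appear as a race/ethnicity difference. With equal racial mixes it would be zero. Which case applies cannot be settled from the documents.

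The documents do not support the inference that chance imbalance by language threatens the primary result: the possible shift is about 1 point or less under an assumed gap, and the power cost is negligible. This is a free improvement with a modest gain, not a flaw that undermines the trial.

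**What to change.** 1. In every pooled model, prespecify language and language-by-time as fixed effects. A language main effect alone would do little for the arm-by-time contrast.
2. Report the race/ethnicity moderator model as planned and also with language and its arm-by-time interaction. Tabulate race/ethnicity by language so that readers can judge how far the two overlap.
3. State whether the language stratification applies to the moderator analyses.
4. Optionally, and only if randomisation is not complete, block on literacy within language. This adds little.

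Items 1 to 3 need only SAP wording and variables already collected at baseline. Item 4 would need separate randomisation lists by language.
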